#### **4.5.10      Electrocardiograms**

All ECG recordings must be performed using a standard, high-quality, high-fidelity, digital ECG machine equipped with computer-based interval measurements. Lead placement should be as consistent as possible.

##### **4.5.10.1      Timing of Electrocardiograms**

Triplicate or single ECG recordings will be obtained at specified timepoints, as outlined in the Schedule of Activities (see [Appendix 1](#)). Triplicate ECG recordings will be obtained within approximately 2-5 minutes of each other.

When triplicate ECGs are required, three interpretable ECG recordings (e.g., without artifacts) must be obtained. Triplicate ECGs will be captured as follows:

- Day 1: Triplicate ECG (pre-dose)
- Week 24: Triplicate ECG (2 hours  $\pm$  30 minutes, post-dose)

The ECG intervals (e.g., PR, QRS, QT, QTcF, and RR) and heart rate from these three ECGs will be entered into the eCRF: in addition, these triplicate readings will be stored for future analysis, if needed.

Single ECG recordings may be obtained at unscheduled and other timepoints as indicated.

##### **4.5.10.2      Patient Preparation for Electrocardiogram**

ECG recordings *are recommended* to not be obtained within 3 hours after any meal, whenever possible. ECG recordings must be performed after the patient has been resting in a supine position for at least 10 minutes. All ECGs *are strongly recommended* to be obtained prior to other procedures scheduled at that same time (e.g., vital sign measurements, blood draws), whenever possible, *except for PROs which should generally be collected first at a visit*. Circumstances that may induce changes in heart rate, including environmental distractions (e.g., television, radio, conversation) should be avoided during the pre-ECG resting period and during ECG recording.

##### **4.5.10.3      Monitoring and Reporting of Electrocardiograms**

For safety monitoring purposes, the investigator must review, sign, and date all ECG tracings. Paper copies of ECG tracings will be kept as part of the patient's permanent study file at the site. Digital recordings will be stored at a central laboratory. The following should be recorded in the appropriate eCRF: heart rate, RR interval, QRS interval, PR duration, uncorrected QT interval, and QTcF based on the machine readings of the individual ECG tracings. Any morphologic waveform changes or other ECG abnormalities must be documented on the eCRF. If considered appropriate by the Sponsor, ECGs may be analyzed retrospectively at a central laboratory.

If at a particular post-dose timepoint, the mean QTcF is  $> 500$  msec and/or 60 msec longer than the baseline value, another triplicate ECG must be recorded, ideally within

the next 5 minutes, and triplicate ECG monitoring should continue at least hourly until the QTcF has stabilized on two successive ECGs. The Medical Monitor should be notified. SOC treatment may be instituted per the discretion of the investigator. If a PK sample is not scheduled for that timepoint, an unscheduled PK sample should be obtained. A decision on study drug discontinuation should be made, as described in Section 5.1. The investigator should also evaluate the patient for potential concurrent risk factors (e.g., electrolyte abnormalities, co-medications known to prolong the QT interval, severe bradycardia).

#### **4.5.11 Patient-Reported Outcomes**

PRO data will be collected via questionnaires to more fully characterize the clinical profile of GDC-0853. The questionnaires, translated into the local language as required, will be completed in their entirety at specified timepoints during the study. To ensure instrument validity and that data standards meet health authority requirements, questionnaires will be self-administered before the patient or clinician receives any information on disease status, prior to the performance of non-PRO assessments, and prior to the administration of study treatment, unless otherwise specified.

Patients and clinicians will use paper based questionnaires to capture PRO data. The instructions for completing the questionnaires will be provided by the investigator staff.

##### **4.5.11.1 Functional Assessment of Chronic Illness Therapy-Fatigue Scale (FACIT Fatigue)**

The FACIT-Fatigue scale will be used to assess patients' fatigue ([Cella et al. 2005](#)). The 13-item questionnaire has been validated for use with SLE patients and has a 7-day recall period. Items are assessed on a 5-point Likert scale with responses ranging from 0 "not at all" to 4 "very much" and possible total scores range from 0 to 52. A higher score indicates less fatigue, and the minimal important different has been identified at a change of  $\geq 3$  points ([Lai et al. 2011](#)). See [Appendix 17](#) for a list of questions in the FACIT-Fatigue.

#### **4.5.12 Mandatory Samples for Whole Genome Sequencing**

At participating sites, a blood sample will be collected for DNA extraction to enable whole genome sequencing (WGS). This sample may be sent to one or more laboratories for analysis.

Collection and submission of WGS samples is contingent upon the review and approval of the exploratory research and the WGS portion of the ICF by each site's Institutional Review Board or Ethics Committee (IRB/EC) and, if applicable, an appropriate regulatory body. If a site has not been granted approval for WGS sampling, this section of the protocol (i.e., Section 4.5.12) will not be applicable at that site.

Genomics are increasingly informing researchers' understanding of disease pathobiology. WGS provides a comprehensive characterization of the genome and,

along with clinical data collected in this study, may increase the opportunity for developing new therapeutic approaches. Data will be analyzed in the context of this study but will also be explored in aggregate with data from other studies. The availability of a larger dataset will assist in the identification of important pathways, thus guiding the development of new targeted agents.

For sampling procedures, storage conditions, and shipment instructions, see the laboratory manual.

Blood samples collected for WGS are to be stored until they are no longer needed or until they are exhausted. However, the storage period will be in accordance with the IRB/EC-approved ICF and applicable laws (e.g., health authority requirements).

Patient medical information associated with WGS specimens is confidential and may be disclosed to third parties only as permitted by the ICF (or separate authorization for use and disclosure of personal health information) signed by the patient, unless permitted or required by law.

Given the complexity and exploratory nature of the analyses, data derived from WGS specimens will, generally, not be provided to study investigators or patients unless required by law. The aggregate results of any conducted research will be available in accordance with the effective Sponsor policy on study data publication.

#### **4.5.13      Optional Samples for Research Biosample Repository**

##### **4.5.13.1      Overview of the Research Biosample Repository**

The Research Biosample Repository (RBR) is a centrally administered group of facilities used for the long-term storage of human biologic specimens, including body fluids, solid tissues, and derivatives thereof (e.g., DNA, RNA, proteins, peptides). The collection, storage, and analysis of RBR specimens will facilitate the rational design of new pharmaceutical agents and the development of diagnostic tests, which may allow for individualized drug therapy for patients in the future.

Specimens for the RBR will be collected from patients who give specific consent to participate in this optional research. RBR specimens will be used to achieve the following objectives:

- To study the association of biomarkers with efficacy, adverse events, or disease progression
- To increase knowledge and understanding of disease biology
- To study drug response, including drug effects and the processes of drug absorption and disposition
- To develop biomarker or diagnostic assays and establish the performance characteristics of these assays

#### **4.5.13.2 Approval by the Institutional Review Board or Ethics Committee**

Collection and submission of biological samples to the RBR is contingent upon the review and approval of the exploratory research and the RBR portion of the Informed Consent Form by each site's Institutional Review Board or Ethics Committee (IRB/EC) and, if applicable, an appropriate regulatory body. If a site has not been granted approval for RBR sampling, this section of the protocol (see Section 4.5.13) will not be applicable at that site.

#### **4.5.13.3 Sample Collection**

The following samples will be stored in the RBR and used for research purposes, including, but not limited to, research on biomarkers related to GDC-0853 and lupus:

- Serum and blood for RNA samples collected at screening; Day 1 (pre-dose); Weeks 12, 24, and 48; and flare visit.

For sampling procedures, storage conditions, and shipment instructions, see the laboratory manual.

RBR specimens are to be stored until they are no longer needed or until they are exhausted. However, the RBR storage period will be in accordance with the IRB/EC-approved Informed Consent Form and applicable laws (e.g., health authority requirements).

#### **4.5.13.4 Confidentiality**

Specimens and associated data will be labeled with a unique patient identification number.

Patient medical information associated with RBR specimens is confidential and may be disclosed to third parties only as permitted by the Informed Consent Form (or separate authorization for use and disclosure of personal health information) signed by the patient, unless permitted or required by law.

Given the complexity and exploratory nature of the analyses, data derived from RBR specimens will generally not be provided to study investigators or patients unless required by law. The aggregate results of any conducted research will be available in accordance with the effective Sponsor policy on study data publication.

Data generated from RBR specimens must be available for inspection upon request by representatives of national and local health authorities, and Sponsor monitors, representatives, and collaborators, as appropriate.

Any inventions and resulting patents, improvements, and/or know-how originating from the use of the RBR data will become and remain the exclusive and unburdened property of the Sponsor, except where agreed otherwise.

#### **4.5.13.5 Consent to Participate in the Research Biosample Repository**

The Informed Consent Form will contain a separate section that addresses participation in the RBR. The investigator or authorized designee will explain to each patient the objectives, methods, and potential hazards of participation in the RBR. Patients will be told that they are free to refuse to participate and may withdraw their specimens at any time and for any reason during the storage period. A separate, specific signature will be required to document a patient's agreement to provide optional RBR specimens. Patients who decline to participate will not provide a separate signature.

The investigator should document whether or not the patient has given consent to participate and (if applicable) the date(s) of consent, by completing the RBR Research Sample Informed Consent eCRF.

In the event of an RBR participant's death or loss of competence, the participant's specimens and data will continue to be used as part of the RBR research.

#### **4.5.13.6 Withdrawal from the Research Biosample Repository**

Patients who give consent to provide RBR specimens have the right to withdraw their specimens from the RBR at any time for any reason. If a patient wishes to withdraw consent to the testing of his or her specimens, the investigator must inform the Medical Monitor in writing of the patient's wishes through use of the appropriate RBR Subject Withdrawal Form and, if the trial is ongoing, must enter the date of withdrawal on the RBR Research Sample Withdrawal of Informed Consent eCRF. The patient will be provided with instructions on how to withdraw consent after the trial is closed. A patient's withdrawal from Study GA30044 does not, by itself, constitute withdrawal of specimens from the RBR. Likewise, a patient's withdrawal from the RBR does not constitute withdrawal from Study GA30044.

#### **4.5.13.7 Monitoring and Oversight**

RBR specimens will be tracked in a manner consistent with Good Clinical Practice by a quality-controlled, auditable, and appropriately validated laboratory information management system, to ensure compliance with data confidentiality as well as adherence to authorized use of specimens as specified in this protocol and in the Informed Consent Form. Sponsor monitors and auditors will have direct access to appropriate parts of records relating to patient participation in the RBR for the purposes of verifying the data provided to the Sponsor. The site will permit monitoring, audits, IRB/EC review, and health authority inspections by providing direct access to source data and documents related to the RBR samples.

## **4.6 PATIENT, TREATMENT, STUDY, AND SITE DISCONTINUATION**

### **4.6.1 Patient Discontinuation**

Patients have the right to voluntarily withdraw from the study at any time for any reason. Reasons for withdrawal from the study may include, but are not limited to, the following:

- Patient withdrawal of consent at any time
- Any medical condition that the investigator or Sponsor determines may jeopardize the patient's safety if he or she continues in the study
- Investigator or Sponsor determines it is in the best interest of the patient
- Patient non-compliance, as per Principal Investigator's discretion

Every effort should be made to obtain information on patients who withdraw from the study. The primary reason for withdrawal from the study should be documented on the appropriate eCRF. However, patients will not be followed for any reason after consent has been withdrawn. Patients who withdraw from the study will not be replaced.

If possible, the investigator will clarify the following:

- If the patient withdrew consent for the remaining study procedures *only* OR
- If the patient withdrew consent for the remaining study procedures as well as the use of all banked samples OR
- If the patient withdrew consent for the remaining study procedures as well as all use of study acquired clinical and laboratory data

If a patient discontinues the study prior to the Week 48 treatment completion visit, an early termination visit should be conducted. These patients should return for the 8-week safety follow-up visit in this study (see [Appendix 1](#)). If the patient is unable to return for a follow-up visit, the trial site may contact the patient by telephone to determine their clinical status.

Patients who discontinue the study during the safety follow-up period but prior to completion of the 8-week safety follow up will be asked to return to the clinic within 30 days ( $\pm 7$  days) after the last dose of study drug or last scheduled visit for an early termination visit.

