### **4.6.2 Study Treatment Discontinuation**

Patients must discontinue study treatment (and will continue in the study) if they experience any of the following:

- Requirement of any prohibited medication as defined in [Section 4.4.2](#)
- Treated with accepted immunosuppressive that exceeds the maximum dose as defined by the protocol (see [Section 4.4.1](#))
- Combination immunosuppressive medications not allowed in the inclusion and exclusion criteria (see [Section 4.1](#))

- Grade >2 AST or ALT elevation: (AST or ALT >3×ULN) in combination with total bilirubin >2×ULN or clinical jaundice as defined by Hy's law
- Grade ≥3 AST or ALT elevation: (AST or ALT >5×ULN)
- Grade 4 Neutropenia: ANC <500/mm^3
- Grade 4 Lymphopenia: absolute lymphocyte count (ALC) <200/mm^3
- Grade 4 Thrombocytopenia: platelet count <25,000/mm^3
- Pregnancy
- Malignancy (with the exception of non-serious local and resectable basal or squamous cell carcinoma of the skin)
- An episode of torsade de pointes

Patients must discontinue study treatment if they receive any new or increased dose of SLE treatment that is not specifically permitted in this protocol (see Section 4.4.1) and approved by the Medical Monitor.

Investigators may discontinue study treatment for:

- Any medical condition that may jeopardize the patient's safety if he or she continues on study treatment
- The best interest of the patient
- Patient non-compliance

If study treatment is discontinued prematurely, patients will be asked to stay in the study and continue with all scheduled visits for the remainder of the 48-week treatment period.

The primary reason for study treatment discontinuation should be documented on the appropriate eCRF. Patients who discontinue study treatment prematurely will not be replaced.

In some cases, study treatment may be resumed if approved by both the investigator and the Medical Monitor.

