**Table 4 Guidelines for Management of Study Treatment in Patients Who Experience Specific Adverse Events (cont.)**

Event	Action to Be Taken a
Vascular Inflammation	
Treatment emergent vasculitis	Initiate appropriate evaluation and consult with the Medical Monitor.

ALP=alkaline phosphatase; ALT=alanine aminotransferase; ANC=absolute neutrophil count; AST=aspartate aminotransferase; CBC=complete blood count; ECG=electrocardiogram; IV=intravenous; OLE=open label extension; PLT=platelet count; SLE=systemic lupus erythematosus; ULN=upper limit of normal.

Note: “Study treatment” includes study drug (GDC-0853 or placebo)

- a Patients who discontinue study drug treatment due to an adverse event should remain in the blinded study if feasible however they will not be eligible for an OLE, if initiated. If they discontinue the study, the patient should enter safety follow up.
- b Appropriate laboratory investigations, including but not limited to cultures, should be performed to establish the etiology of any serious infection.
- c Patients withdrawn from the study due to a reduced neutrophil count must be followed closely for signs of infection, with treatment and repeated laboratory analysis as deemed appropriate by the investigator including discontinuation of other treatments if indicated.
- d Patients withdrawn from the study due to a reduced platelet count should have additional management and treatment as deemed appropriate by the investigator including discontinuation of other treatments if indicated.
- e In rare circumstances, it may be acceptable to resume study drug, provided that any ECG abnormalities have resolved and that the patient is appropriately monitored. Prior to re-administering drug, consult with the Medical Monitor. Clinical judgment should be applied.

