### **6.2 SUMMARIES OF CONDUCT OF STUDY**

The final analysis will be based upon patient data collected through patient discontinuation or study discontinuation, whichever occurs first. The number of patients who enroll, discontinue, or complete the study will be summarized. Reasons for premature study withdrawal will be listed and summarized. Enrollment and major protocol deviations will be listed and evaluated for their potential effects on the interpretation of study results. All summaries will be presented according to randomized treatment assignment.

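### Non-compliance and the patient's best interest are grounds both for leaving the study (4.6.1) and for stopping study drug only (4.6.2), so an observable Week 48 SRI-4 can be lost at the investigator's discretion

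*Combined protocol and SAP*

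**What the plan says.** Section 4.6.1 gives an open list of four example reasons for leaving the study. One is withdrawal of consent. The second is a medical ground: "Any medical condition that the investigator or Sponsor determines may jeopardize the patient's safety if he or she continues in the study". The third turns on benefit and is worded as follows: "Investigator or Sponsor determines it is in the best interest of the patient". The fourth, which is left to the site, is "Patient non-compliance, as per Principal Investigator's discretion". A patient who leaves before Week 48 is to have an early termination visit and return for the 8-week safety visit. Leavers are not replaced.

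Section 4.6.2 has its own discretionary list, for stopping study treatment. Its medical ground is "Any medical condition that may jeopardize the patient's safety if he or she continues on study treatment". Beside it stand a benefit ground, given as "The best interest of the patient", as well as non-compliance. What follows is different: "If study treatment is discontinued prematurely, patients will be asked to stay in the study and continue with all scheduled visits", to the end of the 48-week period.

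Table 4 footnote a says that patients who stop study drug for an adverse event should stay in the blinded study where feasible. Footnote c reads "Patients withdrawn from the study due to a reduced neutrophil count must be followed closely for signs of infection", and footnote d is worded similarly for platelets.

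Section 6.2 bases the final analysis on "patient data collected through patient discontinuation or study discontinuation, whichever occurs first". Section 6.4 analyses all randomized patients, and the primary endpoint is SRI-4 response at Week 48.

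**The concern.** Two sites can face the same non-compliant patient. One ends the patient's participation under 4.6.1; the other stops study drug under 4.6.2 and keeps the visits. Both comply with the protocol. The first yields no Week 48 SRI-4 and the second can yield one.

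The analysis is by intention to treat at a fixed week, so whether the outcome exists should not depend on which section a site happens to apply. A lost outcome must be imputed or dropped although the patient may have been willing to attend. If the losses fall unequally across arms, for instance because non-compliance follows poor tolerability, the difference in response rates is biased. Section 6.1 states no dropout allowance.

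**Working it through.** **Step 1: the grounds side by side.**

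| Ground | 4.6.1: leave the study | 4.6.2: stop study drug only | Separating criterion |
|---|---|---|---|
| Withdrawal of consent | Yes | No | Not needed |
| Medical condition | Risk from continuing in the study | Risk from continuing on study treatment | Yes, the object of the risk differs |
| Best interest of the patient | Yes | Yes | None |
| Non-compliance | Yes | Yes | None |

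The overlap without a criterion is two grounds, not all of them.

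**Step 2: what each route records.** Appendix 1 schedules SLEDAI-2K, BILAG and the Physician's Global Assessment at both Week 48 and the early termination visit. The early termination visit captures the SRI components at exit, which is not the Week 48 endpoint.

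**Step 3: how a lost value is scored.** Section 6.1 makes a patient a non-responder only if there is no post-baseline response assessment. A leaver with earlier visits but no Week 48 value falls outside that rule. Section 6 defers missing-data handling to the DAP, which is not among the documents. Scoring as non-response is therefore an assumption below.

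**Step 4: reproduce the plan's power.** Inputs from Section 6.1: 240 patients at 1:1:1, so 80 per arm; 50% response on placebo; a 25-point improvement, so 75% on active; two-sided 0.05. Exact power of Fisher's test is 88.3%, against the stated figure of about 88%.

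**Step 5: what a loss could do.** Assumptions, none of them in the documents: a fraction L of an arm leaves who could have been followed; half of them would have responded; missing Week 48 counts as non-response. Then

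observed rate = true rate − 0.5 × L.

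For a 6% loss on active and 2% on placebo: 0.75 − 0.5 × 0.06 = 0.72, and 0.50 − 0.5 × 0.02 = 0.49.

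| Loss, active vs placebo | Observed rates | Difference | Fisher power, 80 per arm |
|---|---|---|---|
| None | 75% vs 50% | 25 points | 88.3% |
| 5% vs 5% | 72.5% vs 47.5% | 25 points | 87.1% |
| 3% vs 1% | 73.5% vs 49.5% | 24 points | 84.8% |
| 6% vs 2% | 72% vs 49% | 23 points | 80.8% |
| 10% vs 5% | 70% vs 47.5% | 22.5 points | 78.0% |

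The assumption about leavers matters. If they would instead have responded at their own arm's rate, an equal 5% loss gives 0.75 × 0.95 = 71.25% vs 0.50 × 0.95 = 47.5%, a difference of 23.75 points and power of 82.9%.

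**The case against.** The strongest reply is that retention is already the default. Section 4.6.2 asks patients off drug to keep their visits, Section 4.3.2.3.4 does the same for patients treated beyond escape therapy, and footnote a prefers it after adverse events. Section 4.6.1 only lists examples and directs nobody to withdraw. This stands for patients who have been put on the treatment-only route. It does not help with choosing the route: nothing tells an investigator to stop drug before ending participation, and footnote a's preference does not reach non-compliance or best interest.

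Three stronger readings are tempting, and the documents do not support them.

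- *That all the shared grounds are the same.* The medical-condition items test different things, as Step 1 shows.
- *That Table 4 sends cytopenic patients out of the study.* Footnotes c and d describe care for patients who have been withdrawn; they do not direct withdrawal. Footnote a covers the whole action column, and 4.6.2 keeps patients with Grade 4 neutropenia or thrombocytopenia in the study. What remains is loose wording at odds with both.
- *That power falls to 78–85%.* Those figures come from an assumed arm imbalance. The documents show no imbalance, the study is double-blind, and the equal-loss row shows little effect under the same model.

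Section 4.6.1 also asks for every effort to obtain information on leavers. That narrows the loss but schedules no Week 48 assessment. The study calls itself hypothesis-generating, which lowers the stakes of a power loss but does not make a biased estimate more useful.

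**Conclusion.** The point holds for two grounds, non-compliance and best interest. For each, the protocol offers two routes with different follow-up and nothing to choose between them, so an observable Week 48 SRI-4 can be lost from the intent-to-treat analysis at the investigator's discretion. The medical-condition grounds need a clearer boundary but are not the same test, and footnotes c and d are a wording inconsistency.

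The size cannot be settled from the documents, which give no withdrawal rate and no scoring rule for a leaver with earlier visits. Under the Step 5 assumptions, an equal 5% loss costs about one point of power and leaves the difference unchanged. The unequal losses shown reduce the difference by 1 to 2.5 points and power to about 85% to 78%. These are illustrations, not forecasts. The change is worth making because it is cheap and protects the primary endpoint.

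**What to change.** 1. In 4.6.1, remove non-compliance as a ground for leaving the study. State that it acts on study treatment only, under 4.6.2, with scheduled visits and SRI-4 assessments kept to Week 48 unless the patient withdraws consent.
2. Reconcile the best-interest and medical-condition grounds in 4.6.1 and 4.6.2 by stating what separates ending participation from ending study drug. Keep a safety ground in 4.6.1: limiting withdrawal to consent, loss to follow-up and death would remove a patient protection, and is not proposed.
3. Reconcile Table 4 footnotes c and d with footnote a and 4.6.2.

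None of this alters when study drug is stopped, and no new sample size is needed. The cost is amendment wording plus already scheduled visits for a few more patients off study drug.
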